#### **Summary of Changes in Amendment 1**

The EN3835-224 Protocol was revised with the following changes:

- Text in Sections 1.1 (Synopsis: Overall Design) and 4.1 (Study Design: Overall Design was revised from:
  - ...up to 21 days...

to:

...up to 21 28 days...

• Text in Section 1.1 (Synopsis: Overall Design) was revised from:

The duration of the study from first subject first visit to last subject last visit will be dependent on the ability of the sites to identify and enroll eligible subjects. The entire study is expected to require approximately 12 months to complete.

to:

The duration of the study from first subject first visit to last subject last visit will be dependent on the ability of the sites to identify and enroll eligible subjects. The entire study is expected to require approximately 12 months to complete, however, the duration of the study may be changed due to possible COVID-19 impacts.

- Figure 1 in Section 1.2 was revised to remove text describing assessments to be performed and intervals for treatment.
- Table 1 in Section 1.3 (Schedule of Activities) was revised by changing header for screening from (Day -21 to Day -1) to (Day -28 to Day -1).

- Table 1 in Section 1.3 (Schedule of Activities) footnote g was added to the Hexsel CSS Subsection D Activities column. Subsequent footnotes in the table were renumbered.
- Table 1 in Section 1.3 (Schedule of Activities) original footnote i (now j) was revised from:

• Table 1 in Section 1.3 (Schedule of Activities) original footnote k (now l) was revised from:

At the Day 28 and Day 84 visits, the investigator has the option to skip treatment or proceed with a treatment session for a new sub-area. to:

At the **Treatment Phase visits after** Day 1 <del>28 and Day 84 visits</del>, the investigator has the option to skip treatment or proceed with a treatment session for a new sub-area..

• Text in Section 4.1 (Study Design: Overall Design) was revised from:

The study is expected to enroll subjects over a 3-month period. The entire study is expected to require approximately 12 months to complete.

to:

The study is expected to enroll subjects over a **period of approximately** 3 months <del>period</del>. The entire study is expected to require approximately 12 months to complete, **however, the duration of the study may be changed due to possible COVID-19 impacts**.

• Text in Section 5.2 (Subject Exclusion Criteria), Criteria 1 was revised from:

Has concurrent diseases that might interfere with the conduct of the study, confound the interpretation of the study results, or endanger the participant's well-being, (eg, evidence or history of malignancy unless there has been no recurrence in at least 5 years since treatment, or any significant hematological, endocrine, cardiovascular, respiratory, renal, hepatic, neurologic, psychiatric or gastrointestinal disease).

to:

Has concurrent diseases that might interfere with the conduct of the study, confound the interpretation of the study results, or endanger the participant's well-being, (eg, evidence or history of malignancy, **other than excised basal cell carcinoma and adequately treated squamous cell carcinoma of skin**, unless there has been no recurrence in at least 5 years since treatment), or any significant hematological, endocrine, cardiovascular, respiratory, renal, hepatic, neurologic, psychiatric or gastrointestinal disease.

• Text in Section 5.2 (Subject Exclusion Criteria), Criteria 10 was revised from: The sponsor's medical monitor will be required to review the results for confirmation of eligibility in the case of any of the following: abnormalities in ECGs indicating corrected QT interval (QTc) prolongation of 470 ms or greater, ST-T wave abnormalities, or evidence of previous infarct, abnormalities in clinical laboratory values involving elevations above the normal range for alanine aminotransferase, total bilirubin, and aspartate aminotransferase.

to:

The sponsor's medical monitor will be required to review the results for confirmation of eligibility in the case of any of the following: abnormalities in ECGs indicating corrected QT interval (QTc) prolongation of 470 ms or greater, <del>ST T wave</del> abnormalities, or evidence of previous infarct, abnormalities in clinical laboratory values involving elevations above the normal range for alanine aminotransferase, total bilirubin, and aspartate aminotransferase.

• Text in the last sentence of the second paragraph of Section 5.4 (Screen Failures) was revised from:

The period from the start of screening related procedures at the Screening Visit to the Day 1 Visit must not exceed 21° days, inclusive of any repeat screening procedures.

to:

to:

The period from the start of screening related procedures at the Screening Visit to the Day 1 Visit must not exceed 21-can last up to 28 days, inclusive of any repeat screening procedures.

• Text in the first paragraph of Section 6.3 (Selection of Treatment Regions and Treatment Intervals) was revised from:

During the 6 scheduled visits in the Treatment Phase, the investigator will determine the total number of treatments the subject will receive.

During the 6 scheduled visits in the Treatment Phase, the investigator will determine the total number of treatments the subject will receive.

encourage subjects to complete all 6 scheduled **Treatment Phase** visits and all visit activities in the Treatment Phase **as per the Schedule of Activities**.

- Text in Section 6.3 (Selection of Treatment Regions and Treatment Intervals) item 1 on the list was revised from:
  - 1. The area selected for injection into the thigh will be in the posterolateral portion and will avoid the area of the inferior margin of the intragluteal fold to the upper popliteal crease (inferior to the gluteal sulcus/horizontal crease and the posterior upper thigh).

- 6. Execute the option to proceed, or not to proceed, with a treatment on Day 28. A decision not to proceed with treatment will be based on one, or both, of the following criteria being met:
  - a. No new sub-area identified to be treated.
  - b. Presence of moderate or severe ongoing injection site reactions in the overall treatment area.

- to:
- 1. The area selected for injection into the thigh will be in the posterolateral portion and will avoid the area of the inferior margin of the intragluteal fold to the upper popliteal crease (inferior to the gluteal sulcus/horizontal crease and the posterior upper thigh) and the upper popliteal crease.

- Execute the option to proceed, or not to proceed, with a treatment on Treatment
- 6. Execute the option to proceed, or not to proceed, with a treatment on I reatment Phase visits after Day 1 28. A decision not to proceed with treatment will be based on one, or both, of the following criteria being met:
  - a. No new sub-area identified to be treated.
  - b. Presence of moderate or severe ongoing injection site reactions in the overall treatment area.
- The text in the first paragraph of Section 8.1 was revised from:

All subjects will have eligibility photographs of the mid-back to mid-thigh taken during screening that will be submitted to a sponsor designated reviewer to confirm eligibility.

to:

All subjects will have eligibility photographs of the mid-back to mid thigh taken during screening that will be submitted to a sponsor designated reviewer to confirm eligibility. As part of eligibility confirmation investigators will submit photographs of either the thighs, or the buttocks, to the sponsor for consideration as an overall treatment area. The sponsor-designated central reviewer will only review for the submitted treatment area. If the subject is determined to be ineligible by the central reviewers for the selected treatment area, the investigator may submit photographs of the other treatment area from the same subject for reconsideration of eligibility. The sponsor can provide additional clarification for reconsideration of eligibility of a subject.

• The text in the last paragraph of Section 8.1 was revised from:

Inclusion/exclusion criteria will be re-reviewed at Visit 1 prior to dosing on Day 1. Only subjects deemed eligible by the sponsor designated reviewer will be allowed to proceed with screening activities and receive study treatment. All photographs from this study are the property of Endo and de-identified images may be utilized for

clinical development, scientific communication, marketing, regulatory purposes, and/or legal applications as required/desired by Endo.

to:

Inclusion/exclusion criteria will be re-reviewed at Visit 1 prior to dosing on Day 1. Only subjects deemed eligible by the sponsor-designated reviewer will be allowed to proceed with screening activities and receive study treatment. **Subjects deemed ineligible in the overall submitted treatment area(s) by the sponsor-designated reviewer will be considered screen failures (note that at least 1 submitted treatment area must be determined as eligible for a subject to be enrolled).** Subjects deemed ineligible by the sponsor designated reviewer will be considered <del>screen failures.</del> All photographs from this study are the property of Endo and deidentified images may be utilized for clinical development, scientific communication, marketing, regulatory purposes, and/or legal applications as required/desired by Endo.

 Text in Section 8.2.1.6 (Hexsel Cellulite Severity Scale) was revised from: This assessment will be conducted at the Screening Visit and all study visits.

• Text in Section 8.3.6 (Electrocardiogram) was revised from:

If the ECG report shows a QTc prolongation of 470 ms or greater, ST-T wave abnormalities, or evidence of previous infarct, the investigator should repeat the ECG within 1 hour.

to:

If the ECG report shows a QTc prolongation of 470 ms or greater, ST T wave abnormalities, or evidence of previous infaret, the investigator should repeat the ECG within 1 hour.

## 1. **PROTOCOL SUMMARY**

#### 1.1. Synopsis

Name of Sponsor/Company: Endo Pharmaceuticals Inc.

Name of Investigational Product: CCH

Name of Active Ingredient: Collagenase Clostridium Histolyticum

**Title of Study:** A Phase 2 Multicenter, Open-label, Randomized, Parallel-group, Multiple-dose study to Assess the Effectiveness, Safety and Satisfaction with Collagenase Clostridium Histolyticum Grid Technique Injections of Buttock or Thigh Cellulite with Laxity in Adult Females

**Phase of development:** Phase 2

#### **Study period:**

Estimated date first subject enrolled: 01 October 2020 Estimated date last subject completed: 01 June 2021

#### **Objectives and Endpoints: Objectives** Endpoints **Primary** To assess the efficacy of CCH for the • Proportion of 1-level responders (+1 or • treatment of cellulite in the presence of better score) on the I-GAIS for either dermal laxity using the Investigator buttock or either thigh at Day 180 Global Aesthetic Improvement Scale (I-GAIS) Secondary To assess the efficacy of CCH for the Proportion of 1-level responders (+1 or • • treatment of cellulite in the presence of better score) on the I-GAIS for either buttock or either thigh at Study Days 28, dermal laxity using the I-GAIS 56, 84, 112, and 140 I-GAIS ratings at Study Days 28, 56, 84, • 112, 140, and 180 • To assess the efficacy of CCH for the • Proportion of 1-level responders (+1 or treatment of cellulite in the presence of better score) on the Subject Global Aesthetic Improvement Scale (S-GAIS) dermal laxity using subject assessments for either buttock or either thigh at Study Days 28, 56, 84, 112, 140, and 180 The change from baseline to Day 180 in the Body-O Appraisal of the individual item cellulite scores and total score. To assess the effectiveness of CCH for The change from baseline to each Study • the treatment of cellulite in the presence Visit (Day 28 through the Day 180 Visit) of dermal laxity using Subsection D of in Hexsel CSS Subsection D severity the Hexsel Cellulite Severity Scale (CSS) score.

• To assess the safety and tolerability of CCH for the treatment of cellulite in the presence of dermal laxity	
 
Proportion (incidence) of subjects reporting each adverse event (AE), treatment-emergent adverse event (TEAE), treatment-related AE, and adverse event of special interest (AESI). Change from baseline reported at each visit for vital signs, potentially clinically important vital signs, clinical laboratory tests, and potentially clinically important laboratory tests.
 

• To assess the immunogenicity of CCH in the treatment of cellulite in the presence of dermal laxity	
 
Anti- Clostridial class I collagenase (AUX-I) and Anti- Clostridial class II collagenase (AUX-II) antibody levels
 
Neutralizing antibodies to AUX-I and AUX-II
 

•	
•	•

#### **Overall Design:**

This is a Phase 2, open-label, randomized, parallel-group, multiple-dose, safety and effectiveness study designed to evaluate 2 different CCH dose concentrations and aliquot volumes delivered via uniform grid injection techniques in female subjects presenting with both mild to moderate cellulite and moderate to severe dermal laxity of the buttocks, or thighs, and with a body mass index 18 to < 29.9kg/m^2 (normal or overweight).

Following determination of eligibility based on photography and Inclusion/Exclusion assessment, the investigator will propose each eligible subject for treatment of either both buttocks, or both thighs. A sponsor-designated reviewer will confirm subject eligibility for thighs or buttocks treatment based on review of screening images of areas to be treated. Prior to randomization, the sponsor will categorize the thighs or buttocks of each eligible subject for the following characteristics: mild cellulite with moderate dermal laxity, moderate cellulite with severe dermal laxity, moderate cellulite with moderate dermal laxity and moderate cellulite with severe dermal laxity. This pre-randomization cohort management process is intended to try to ensure enrollment of the desired scope of study participants. Subjects will then be randomized to receive treatment in either Cohort A (Uniform 0.1-mL 1-Aliquot GRID injection technique) or Cohort B (Uniform 0.3-mL 2-Aliquot GRID injection technique) in a 1:1 ratio.

During the 6 scheduled Treatment Phase visits the investigator will determine the total number of treatments the subject will receive, and can incrementally treat new sub-areas at consecutive Treatment Phase visits. Specific injection sites (sub-areas) within the overall treatment area will not be dosed more

frequently than every 56 days.

Subjects will return to the study site for all 6 scheduled Treatment Phase visits to complete assessments, even if not receiving treatment during the visit.

Subjects will participate in the study for approximately 29 weeks, including a screening period of up to 28 days. The duration of the study from first subject first visit to last subject last visit will be dependent on the ability of the sites to identify and enroll eligible subjects. The entire study is expected to require approximately 12 months to complete however, the duration of the study may be changed due to possible COVID-19 impacts.

Disclosure Statement: This is an open-label safety and efficacy study with 2 treatment cohorts.

#### Number of Subjects (planned):

Approximately 32 subjects will be enrolled into the study such that approximately 24 evaluable subjects complete the study.

#### **Treatment Groups and Duration:**

Subjects will be randomized to treatment (for both of their treatment areas) to either Cohort A or Cohort B in a 1:1 ratio.

The total amount of CCH to be administered per subject over the course of the study will not exceed 10.08 mg.

Data Monitoring Committee: No data monitoring committee will be used for this study.

## 1.2. Study Schema

#### Figure 1: Study Design Overview

Subject will receive at least 3 and up to 6 treatment sessions (both buttocks or both thighs) Sub-areas that are treated within each overall treatment area will not be dosed more frequently than every 56 days

aThe investigator has the option to skip the treatment session

## **1.3.** Schedule of Activities

#### Table 1:Schedule of Activities

	Screening			Treatme	ent Phase a			Follow-up
Activities	(Day -28 to Day -1)	Day 1 Visit 1	Day 28 (±3 day) Visit 2	Day 56 (±3 day) Visit 3	Day 84 (±3 days) Visit 4	Day 112 (±3 days) Visit 5	Day 140 (±3 days) Visit 6	Day 180 End of Study/ Early Termination Visit (±10 days)
Informed consent b	X							
Inclusion/exclusion criteria review	X	Xc						
		Х	Х	Х	Х	Х	Х	X
Imaging for eligibility confirmation d	X							
Medical and cellulite history (including previous treatment)	Х							
Physical examination	X							X
Height	X							
Weight	X	Х						X
Fitzpatrick skin type	X							
Vital signs e	X	Х	Х	Х	Х	Х	Х	X
12-lead ECG	X							Х
Clinical safety laboratories	X							X
Anti-AUX-I/Anti-AUX-II antibody level sample		Х						Х
Serum pregnancy test	X							X
Urine pregnancy test		Х	Х	X	Х	X	Х	
CR-PCSS	X							
I-GAIS f			Х	Х	Х	Х	Х	Х
S-GAIS f			Х	Х	Х	Х	Х	Х

Table 1:	Schedule of Activities	(Continued)
----------	------------------------	-------------

	Screening	Screening Treatment Phase a						
Activities	(Day -21 to Day -1)	Day 1 Visit 1	Day 28 (±3 day) Visit 2	Day 56 (±3 day) Visit 3	Day 84 (±3 days) Visit 4	Day 112 (±3 days) Visit 5	Day 140 (±3 days) Visit 6	Day 180 End of Study/ Early Termination Visit (±10 days)
Body-Q		Х						Х
Hexsel CSS Subsection D g	X h	Х	Х	Х	X	Х	Х	X
Assignment of treatment area (buttocks or thighs)	х							
Confirm eligibility		Х						
Randomize treatment arm		Х						
Digital photography k		Х	Х	Х	X	Х	Х	X
Study intervention administration		X 	X 	X 	X 	X 	X 	
Prior/Concomitant medications/procedures	Collect throughout the study							
AEs	Collect throughout the study							

a During unscheduled visits the investigator or designee may perform any study procedure deemed clinically necessary (eg, vital signs, clinical laboratory assessments, pregnancy test, etc).

b Performed prior to any study-required assessments.

c Should be reassessed and verified prior to dosing.

d All subjects will have photographs of the mid-back to mid-thigh taken during screening that will be submitted to a sponsor-designated reviewer to confirm eligibility. For these eligibility confirmation photographs the subject will be standing in a consistent, standardized relaxed standing pose (ie, standing position with relaxed gluteus muscles) and will be wearing a standardized photographic garment. Specific instructions for taking the eligibility confirmation photographs as well as for providing them to, and receiving confirmation (or lack thereof) from, the sponsor-designated reviewer will be provided in the Study Operations Manual.

e On treatment phase visit days (Days 1, 28, 56, 84, 112, and 140) vital signs will be taken up to 4 hours prior to dosing and at 15 minutes and 30 minutes after dosing (body temperature is not required at the 15 minute postdose time point).

#### EN3835-224 Protocol Amendment 1

These assessments, which will be based on digital photographs, are performed separately for each of 2 treatment areas and must be completed before study intervention administration on those visits. If at a treatment visit, use photographs taken before marking treatment area.	
Subjects with Hexsel CSS Subsection D score greater than 3 at screening are excluded. A score greater than 3 is defined as an appearance significantly worse	
than exhibited in the Hexsel CSS Subsection D severe (score = 3) image.	
Collected after treatment on Study Day 1 and is assessed for the overall subject and not per treatment areas.	
Photographs will be taken before and after marking the treatment areas.	
For subjects not receiving treatment during a treatment phase visit a photograph will be taken but no marking will be done and no postmarking photograph will be taken. Please see the Photography Manual for details.	9
Subjects will receive at least 3, and up to 6 treatment sessions. The investigator will determine the total number of treatments the subject will receive and can	
more frequently than every 56 days. At the Treatment Phase visits after Day 1, the investigator has the option to skip treatment or proceed with a treatment	
session for a new sub-area.	
	1
After treatment subjects will be provided with compression garments that they will be	e

required to wear.

AE=Adverse event; CR-PCSS=Clinician-reported Photonumeric Cellulite Severity Scale; CSS= Cellulite Severity Scale; ECG=Electrocardiogram; I-GAIS=Investigator Global Aesthetic Improvement Scale; S-GAIS=Subject Global Aesthetic Improvement Scale

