## Table 2:Intended Distribution of Subject Treatment Area Characteristics and
Locations

Note: A total of 32 subjects are expected to contribute a total of 64 treatment areas. Each subject's 2 treatment areas may be allocated to different categories according to the severity of cellulite and severity of dermal laxity.

Subjects will then be randomized to treatment with either Cohort A (Uniform 0.1-mL 1-Aliquot GRID injection technique) or Cohort B (Uniform 0.3-mL 2-Aliquot GRID injection technique) in a 1:1 ratio.

The treatment cohorts will differ in concentrations/aliquot volumes/number of aliquots per injection but neither cohort will exceed the maximum total dose per treatment area (up to 0.84 mg per each buttock or thigh) per treatment session. Details of the injection techniques can be found in the Study Operations Manual.

. Subjects will return to the study site for all 6 scheduled visits and all visit activities in the Treatment Phase.

This study is planned to be conducted at approximately 2 study sites. Subjects may participate in the study for a total of up to approximately 29 weeks, including a screening period of up to 28 days, an active treatment period of 20 weeks and a Follow-up Visit 40 ( $\pm$  10) days after the last dose of study drug. A minimum of 24 evaluable subjects are required for the primary analysis. The duration of the study from first subject first visit to last subject last visit will be dependent on the ability of the sites to identify and enroll eligible subjects. The study is expected to enroll subjects over a period of approximately 3-months. The entire study is expected to require approximately 12 months to complete, however, the duration of the study may be changed due to possible COVID-19 impacts.

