## 4.4. End of Study Definition

A subject is considered to have completed the study if the subject has completed the Day 180 End of Study Visit.

The end of the study is defined as the completion of the final assessment for the last subject enrolled in the trial.

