## 6.3. Selection of Treatment Regions and Treatment Intervals

During the 6 scheduled visits in the Treatment Phase, the investigator will determine the total number of treatments the subject will receive.

complete all 6 scheduled Treatment Phase visits and all visit activities in the Treatment Phase as per the Schedule of Activities. During a subject's treatment session the investigator will:

- 1. Identify and mark sub-areas to be treated in each treatment area. The area selected for injection into the thigh will be in the posterolateral portion and will avoid the area of the inferior margin of the intragluteal fold (inferior to the gluteal sulcus/horizontal crease and the posterior upper thigh) and the upper popliteal crease. Additional information on the treatment area selection and marking are described in the Study Operations Manual.
- 2.
- 3. Administer up to 0.84 mg CCH in each treatment area, at each treatment phase visit; with actual dose administered at each treatment visit clearly captured.

The actual number of injections administered at each treatment visit should be clearly captured.

- 5.
- 6. Execute the option to proceed, or not to proceed, with a treatment on Treatment Phase visits after Day 1. A decision not to proceed with treatment will be based on one, or both, of the following criteria being met:
  - a. No new sub-area identified to be treated.
  - b. Presence of moderate or severe ongoing injection site reactions in the overall treatment area.
- 7. At any treatment phase visit after Day 1, if, in the investigator's clinical judgment, the clinical presentation of a subject's cellulite dimples with dermal laxity is found satisfactory or resolved, the investigator may choose to stop further treatment.

All subjects must complete all 6 scheduled Treatment Phase visits at Days 1, 28 ( $\pm$ 3), 56 ( $\pm$ 3), 84 ( $\pm$ 3), 112 ( $\pm$ 3), 140 ( $\pm$ 3), and 180 ( $\pm$ 10) regardless of the number of treatment sessions. After the completion of a treatment session the investigator or qualified designee will apply a sterile dressing to the injection areas with hypoallergenic tape. The subject will be instructed to remove the dressing in the evening. Following treatment, the subjects will be provided with compression garments that must be worn. Refer to the Study Operations Manual for additional guidelines on the use of compression garments.

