## 6.8. Study Treatment Modification

At any visit after Day 1, the investigator can choose not to continue treatment if there are moderate or severe ongoing injection site reactions in the overall treatment area or if there are no new areas to treat, or if the cellulite and laxity have sufficiently resolved.

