The study is expected to enroll subjects over a period of approximately 3 months. Subjects will participate in the study for approximately 29 weeks, including a screening period of up to 28 days. The entire study is expected to require approximately 12 months to complete. However, the duration of the study may be changed due to possible COVID-19 impacts.

Subject will receive at least 3 and up to 6 treatment sessions (both buttocks or both thighs)  
Sub-areas that are treated within each overall treatment area will not be dosed more frequently than every 56 days

aThe investigator has the option to skip the treatment session

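### Do the 3-session minimum, the stopping text and the follow-up timing conflict in a way that affects the Day 180 responder result?

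*Protocol*

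**What the plan says.** **Number of sessions.** The treatment footnote to the Protocol's Schedule of Activities states "Subjects will receive at least 3, and up to 6 treatment sessions". The study schema (Figure 1) carries the same minimum next to the note "The investigator has the option to skip the treatment session". SAP Section 3.1 repeats it: "Subject will receive at least 3 and up to 6 treatment sessions (both buttocks or both thighs").

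**Stopping.** Protocol Section 6.3, item 7, says that if the appearance is judged satisfactory or resolved after Day 1, "the investigator may choose to stop further treatment". Section 6.8 says "At any visit after Day 1, the investigator can choose not to continue treatment" for ongoing moderate or severe injection site reactions, no new area to treat, or sufficient resolution. Neither visible passage mentions a minimum.

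**Follow-up.** Protocol Section 4.1 describes "an active treatment period of 20 weeks and a Follow-up Visit 40" (±10) "days after the last dose of study drug". The Schedule of Activities sets the last visit at Day 180 (±10). Section 6.3 requires every scheduled visit however many sessions were given. Section 4.4 says "A subject is considered to have completed the study if the subject has completed the Day 180 End of Study Visit".

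**Analysis.** SAP 7.7.1.1 gives the Day 180 I-GAIS responder proportion with a Clopper-Pearson interval, by regimen and overall. SAP 7.8.1 summarises injections, sub-areas and subjects treated at each visit by regimen and region, and adds a subject listing of exposure. SAP 6.1 adds listings of all case report form data and derived variables. SAP 7.8.8 groups the immunogenicity results by total sessions received.

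**The concern.** Read literally, the stopping text permits one or two sessions, which the Schedule footnote says should not occur. The Section 4.1 wording, also read literally, would move the follow-up visit for anyone whose last dose came before Day 140.

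The possible cost is interpretive. The Day 180 responder proportion may pool subjects who differ in number of sessions, cumulative dose and time since last dose. Investigators know the assignment and decide on further sessions after randomisation, partly because of injection site reactions, so exposure could differ between regimens. The duration of exposure in SAP Table 19 is the number of minutes from first to last injection within a visit, so it does not describe time on treatment or time since last dose. A reader who sees a regimen difference at Day 180 might want to know whether it goes with a difference in exposure, and no visible table by regimen answers that directly.

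**Working it through.** **1. The 40-day figure.** Inputs: dosing visits at Days 1, 28, 56, 84, 112 and 140 (±3 days, Day 1 fixed) and the final visit at Day 180 (±10), from the Schedule of Activities.

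Nominal gap = 180 − day of last dose. For Day 140 this is 180 − 140 = 40, which reproduces Section 4.1. With both windows, the shortest gap is 170 − (day + 3) and the longest is 190 − (day − 3). For Day 1, where there is no dosing window, they are 170 − 1 and 190 − 1.

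| Last dose | Nominal gap (days) | With windows |
|---|---|---|
| Day 140 | 40 | 27–53 |
| Day 112 | 68 | 55–81 |
| Day 84 | 96 | 83–109 |
| Day 56 | 124 | 111–137 |
| Day 28 | 152 | 139–165 |
| Day 1 | 179 | 169–189 |

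The last two rows arise only if fewer than 3 sessions are given. Only a Day 140 last dose can fall within 30 to 50 days.

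Section 4.1 reads as a summary of a full course: 28 days of screening + 140 days (20 weeks) + 40 days = 208 days = 29.7 weeks, against its stated upper limit of approximately 29 weeks.

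**2. How many treatment patterns are affected.** With Day 1 always treated, there are 2^5 = 32 treat-or-skip patterns. Removing those with one session (1) or two (5) leaves 26. Of these, 2^4 − 1 = 15 end at Day 140, 2^3 − 1 = 7 at Day 112, 2^2 − 1 = 3 at Day 84 and 1 at Day 56. So 11 of the 26 cannot meet the Section 4.1 interval. These are counts of patterns, and the documents give no expected frequencies.

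**3. Whether the session rules exclude each other.** The Schedule footnote sets a floor and allows skipping in the same note. Sections 6.3 and 6.8 are permissive. An investigator who gives at least 3 sessions and then stops complies with all of them. The visible text of Section 6.3 has blank numbered items and lost text next to the sentence on the number of treatments, and SAP 3.1 is blacked out directly after the 56-day rule. The absence of a qualifier there cannot be treated as an omission.

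**4. What the exposure tables leave open.** Take a hypothetical cell of 8 subjects (one regimen, one region) with 8 treated on Day 1 and 4 at each of the five later visits. Sessions total 8 + 5 × 4 = 28, a mean of 3.5. Two arrangements that respect the minimum give the same counts of subjects treated per visit:

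- 4 subjects on Days 1/28/84/140 and 4 on Days 1/56/112: mean gap (4 × 40 + 4 × 68)/8 = 54 days.
- 4 subjects on Days 1/28/56 and 4 on Days 1/84/112/140: mean gap (4 × 124 + 4 × 40)/8 = 82 days.

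With the dose cap of 1.68 mg per session, cumulative maxima are 3 × 1.68 = 5.04 mg or 4 × 1.68 = 6.72 mg in both. If the stopping text alone governed, 4 subjects with six sessions and 4 with Day 1 only would also fit: gap (4 × 40 + 4 × 179)/8 = 109.5 days, with maxima from 1.68 to 10.08 mg.

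So per-visit counts do not determine the per-subject course. The example matches only that one row of SAP 7.8.1; it does not show that the injection and sub-area rows would also match. The planned listings should supply what the counts leave out, because Section 6.3 requires the actual dose at each treatment visit to be captured and Section 6.6 requires dosing information for every subject visit.

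**The case for a change.** The strongest reply is that a listing is not a summary. The sample size section says the study allows a comparison of the two regimens, unblinded investigators choose the number of sessions, and the data for a short table by regimen already exist. Total sessions are even derived for the immunogenicity table. The exposure tables also use the Safety Population while responders are counted in the mITT Population. And if a subject stops after one or two sessions, the visible text does not settle whether that is a protocol deviation.

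Part of this stands. A small table of total sessions, cumulative mg and days from last dose to the Day 180 rating would help a reader, and the wording deserves tidying.

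The rest does not lead to a change. Item 7 of Section 6.3 lets treatment stop because the result is satisfactory, so the number of sessions partly follows response. A table in cells of about 8 could not separate exposure from outcome. The mITT Population leaves out only treated subjects with no valid I-GAIS rating after an injection, who cannot contribute to the Day 180 count, and SAP 7.1 lists those excluded. Under SAP 4.3 the study team classifies deviations before database lock, and because the SAP defines no per-protocol population, that classification removes nobody from the efficacy analysis.

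**Conclusion.** No change to the plan follows. The 40-day phrase in Section 4.1 is a loose summary of a full-length course. It differs from the fixed visit by 28 days nominally for a Day 112 last dose (68 − 40) and by more for earlier ones, but no visit date, endpoint or analysis is taken from it. The missing cross-reference between the session minimum and the stopping text is a matter of wording, since both can be honoured. The sponsor should reconcile these passages editorially; which rule is right is not for this review to say. The absence of a table of sessions, dose and timing by regimen is a reporting preference that the planned listings cover at this sample size.

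This rests on three assumptions: that the listings will carry treatment dates and doses for each subject, that the blacked-out text near these rules does not alter their meaning, and that the Day 180 proportions are read as descriptive, as both documents' sample size sections imply by calling the study exploratory and not powered for a regimen difference. SAP 7.7.3 is redacted and was not judged.
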